#### 8.2.2. Cohort 3 Plasma Infusion

Cohort 3 subjects will be scheduled for 2 infusion visits to occur on Study Days 1 and 15. Because of the crossover, no more than 48 hours prior to administration of a subject's first infusion, he or she will be randomly assigned to a study arm (Arm 5 or Arm 6) indicating the specific product to be administered. The alternate product of what is received at the first Infusion Visit, either FDP (Test) or FFP (Control), will be infused at the second Infusion Visit.

At the time of each scheduled Infusion Visit, the prior activities and procedures must be completed for each subject before infusion may begin:

- Review of medical history, concomitant medications, and AEs since the collection visit(s);
- Conduct a complete physical examination that includes measurement of weight, and vital signs (blood pressure, heart rate, respiration rate, and temperature), and evaluation of cardiopulmonary systems, basic neurological function, and presence of DVT, cardiac ischemia, or PE. DVT will be assessed in conjunction with a subjects' D-dimer test results and Wells scale score (Dupras et al-2013).
- Collect urine and blood samples as noted for all tests listed in the Schedule of Events table (Table 8);
- Cross-match subject's RBCs to FDP or FFP; and
- Reverse ABO type on FDP or FFP.

At the discretion of the PI, a study plasma infusion may not be given if, in the PI's opinion, the subject's clinical status precludes a study plasma infusion and the planned protocol assessments. The reason for the PI's decision to withhold a study plasma infusion will be documented in the source documents and eCRFs. This does not preclude a standard of care plasma infusion.

After reconstitution of the FDP or FFP, a visual examination for signs of lipemia, hemolysis, clotting, or other issues that impact the quality and acceptability of the plasma for re-infusion will be performed. This visual inspection of reconstituted FDP also includes observation of macroscopic particulate matter. Reconstituted FDP or FFP that does not meet visual examination criteria will be discarded per the site's SOP for the destruction of blood and blood products.

The date, start, and stop times of each plasma infusion will be recorded in the source document and eCRF. The scheduled dose of FDP or FFP will be transfused into subjects using a standard plasma administration set according to the clinical site's SOPs. The plasma product will be pumped into the vein at an initial rate of approximately 2-3 mL/minute for the first 10 minutes, and then the rate will be adjusted to not more than 10 mL/minute until completion of the plasma infusion. During the course of the infusion, vital signs (blood pressure, heart rate, respiration rate, and temperature) for all subjects will be monitored every 15 minutes (± 5 minutes) until the infusion is completed.

Subjects will remain at the study site and be actively monitored under direct observation for a minimum of 5 to 6 hours post-infusion. They will be asked about and observed during and after the study plasma infusion for evidence of acute transfusion reactions including: allergic reactions, bradycardia, tachycardia, or other cardiac dysrhythmia, hypertension, hypotension, dyspnea, hemolysis, fever, chills, thromboembolic events, bleeding, and infection.

Vitals will be measured every 30 minutes ( $\pm$  5 minutes) up to 4 hours post-infusion. Measurement of vitals will then be decreased to every 4 hours ( $\pm$  40 minutes) until the subject is released. The following laboratory tests will be performed at 30 minutes ( $\pm$  5 minutes) and at 4 hours ( $\pm$  40 minutes) post-infusion (see Table 9):

- Urinalysis;
- CBC (Hematocrit, Hemoglobin, Platelet Count, RBC Count, WBC Count);
- Chemistry panel (pH, Ionized Calcium and Total Magnesium [at 30 minutest post-infusion only], ALP, ALT, AST, Calcium, Bicarbonate, lactate, Chloride, Glucose, Potassium, Sodium, Total Bilirubin, Total Protein, BUN, and Creatinine);
- PT/INR and aPTT;
- DAT (IgG and C3);
- Coagulation factor tests (Factors I, II, V, VII, VIII, IX, X, XI, D-Dimer, von Willebrand Factor activity, Protein C activity, and Protein S activity); and
- PF 1+2, TAT, AT-III, Alpha-2 Antiplasmin, and C3a des Arg at 30 minutes post-infusion only. These tests are for research purposes only and will not be used to assess subject safety.

Prior to release, subjects will undergo an additional physical evaluation (eg, focus on cardiopulmonary systems, basic neurological function, and presence of DVT). The investigator will interpret exam findings in conjunction with the subjects' 4-hour post-infusion D-dimer test results and Wells criteria to determine the medical suitability for release.

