**Table 8:** Study Events Schedule for Cohort 3

Visit Activities:	Visit 1	Visits 2a-2d P	Visit 3	Visit 4	Phone Calls N	Visit 5	Visit 6	Visit 7	Phone Calls N	Visit 8	Phone Call N	Visit 9
	Screening	Plasmapheresis Collections	Infusion #1	24-Hour Follow- Up	48 & 72 hrs	7-Day Follow- Up	Infusion #2	24- Hour Follow- Up	48 & 72 hrs	7-Day Follow- Up	14-Day	28-Day Follow- Up
Study Day*:	-56 to -49	-55 to -35	1	2	3 & 4	8	15	16	17 & 18	22	29	43
Visit Window:				±3 hrs	± 2 hrs	± 1 day	± 3 days	± 3 hrs	±2 hrs	± 1 day	±2 hrs	± 1 day
General Procedures												
Informed Consent	X											
Inclusion/Exclusio n Criteria	X											
Demographic Questionnaire	X											
AABB Donor History Questionnaire A	X	X										
Duke Activity Status Index	X											
Subject Medical Health Standardized Questionnaire B	X	X	X	X		X	X	X		X		X
Complete Physical Exam C	X		X	X								
Randomization			X									
Abbreviated Physical Exam D		X				X	X	X		X		X
Wells Scale H	X		X	X			X	X				
Vital Signs E	X	X	X H	X		X	$X^{H}$	X		X		X
Concomitant Medications	X	X	X	X	X	X	X	X	X	X	X	X
AEs		X	X	X	X	X	X	X	X	X	X	X
Plasma Collection F		X	_		_						_	

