**Table 8: Study Events Schedule for Cohort 3 (continued)** 

Visit Activities:	Visit 1	Visits 2a-2d P	Visit 3	Visit 4	Phone Calls N	Visit 5	Visit 6	Visit 7	Phone Calls N	Visit 8	Phone Call N	Visit 9
	Screening	Plasmapheresis Collections	Infusion #1	24-Hour Follow- Up	48 & 72 hrs	7-Day Follow- Up	Infusion #2	24- Hour Follow- Up	48 & 72 hrs	7-Day Follow- Up	14-Day	28-Day Follow- Up
Study Day*:	-56 to -49	-55 to -35	1	2	3 & 4	8	15	16	17 & 18	22	29	43
Visit Window:				± 3 hrs	± 2 hrs	± 1 day	± 3 days	±3 hrs	± 2 hrs	± 1 day	± 2 hrs	± 1 day
HIV-1/2, HBV, HCV, & West Nile Virus Nucleic Acid Tests	X											
Cross-match RBC vs. FDP/FFP			X				X					
Reverse Type of FDP/FFP			X				X					
Coagulation Factor Tests M			$X^{J}$				$X_{1}$					
D-Dimer Test	X		$X^{J}$	X			$X^{J}$	X				
Total Protein O		X					X J					
PF 1+2, TAT, AT- III, Alpha-2 Antiplasmin, and C3a des Arg Q			$X_{l}$				X J					

\*The estimated manufacturing time is 5 weeks.

<sup>AThe AABB donor history questionnaire is administered at all donation visits.

<sup>BConfirm data are accurate; subject is healthy with no significant medical history change.

<sup>C Complete physical exams to include height (screening only), weight, vital signsE, and a targeted assessment of health as described in section 7.2 and section 8.2.

<sup>DAbbreviated physical exam to include vital signs E and a general assessment of health.

<sup>EVital signs monitored are blood pressure, heart rate, respiration rate, and temperature. These will be measured every 15 minutes (± 5 minutes) during the infusion, every 30 minutes (± 5 minutes) between 0 and 4 hours post-infusion, and then every 4 hours (± 40 minutes) until the subject is released from the clinic.

<sup>FEach plasmapheresis session is to be scheduled approximately 7-10 days apart. Cohort 3 will require 3 to 4 plasma donation sessions.

<sup>GExit interview may take place at any point during the study and is dependent upon subject's continued enrollment status.

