<sup>HMonitor vital signs every 15 minutes during infusion; every 30 minutes for up to 4 hours post-infusion; and after 6 hours, vital signs should be measured every 4 hours until the subject is released. Subjects assessed for DVT, PE, and cardiac ischemia using the Wells Scale prior to infusion, at 30 minutes, 4 hours, and 24 hours post-infusion before the subject can be released from the clinic.

<sup>1Chemistry panel includes Calcium, ALP, ALT, AST, Bicarbonate, Chloride, Glucose, Potassium, Sodium, Total Bilirubin, Total Protein, BUN, Lactate, and Creatinine. pH, Ionized Calcium and Total Magnesium will only be measured at pre-infusion and 0.5 hour post-infusion.

<sup>JSee Table 9 - Laboratory Testing Schedule and Volumes for Cohort 3 for sampling time points.

KCBC comprises Hematocrit, Hemoglobin, Platelet Count, RBC Count, and WBC Count.

<sup>LSPEP is performed on the donated plasma at each plasmapheresis visit.

MCoagulation testing for Factors I, II, V, VII, VIII, IX, X, XI von Willebrand Factor activity, and Total Protein C and S activity.

N Follow-up phone calls to the subject will be made 48 hours and 72 hours following both Infusion Visits. The 14-day follow-up phone call will only occur after Infusion Visit #2.

<sup>o Total Protein can be performed up to 24 hours prior to each subsequent plasmapheresis session.

PAdditional collection visits may be required in the event that a plasma unit experiences an issue during preparation (eg, leakage during transfer to lyophilization bag) or during lyophilization (eg, bag breakage during freeze-drying).

O These tests are for research purposes only and will not be used to manage the safety of study participants.

Table 9: Laboratory Testing Schedule and Volumes for Cohort 3

Laboratory and Coagulation Factor Testing	Screening	Collection Visits		fusion Visit #1 and #2	ts	24-Hour Follow-Up	7-Day Follow-Up	28-Day Follow-Up
			Pre-	Post-I	nfusion	Visits	Visits	Visit
			Infusion	0.5 hr	4 hrs			
Pregnancy Test (females only)	X		X					
Urine Drug Screening	X							
Urinalysis	X		X	X	X	X		
Chemistry Panel A	X		X	X	X	X	X	
CBC B	X		X	X	X	X	X	X
Hematocrit		X						
PT/INR	X		X	X	X	X		X
aPTT	X		X	X	X	X		X
DAT (IgG and C3)	X		X			X		X
Blood Type for ABO and Rh	X		Xc					
Red-Cell Antibody Screen	X							
Syphilis Screen	X							
HTLV Antibody Screening Test	X							

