### 8.3. Follow-Up Visits

#### 8.3.1. 24-Hour Follow-Up Visit

Subjects in all 3 cohorts should be scheduled for an on-site follow-up visit 24 hours ( $\pm$  3 hours) after the completion of the plasma infusion. During this visit, the following procedures will be performed:

- Review of medical history, concomitant medications, and AEs since the infusion visit;
- Conduct a complete physical examination that includes measurement of, body weight, and vital signs (blood pressure, heart rate, respiration rate, and temperature), and evaluation of cardiopulmonary systems, basic neurological function, and presence of DVT, cardiac ischemia, or PE. DVT will be assessed in conjunction with a subjects' D-Dimer test results and Wells scale score; and
- Collect urine and blood samples as noted for all tests listed in the Schedule of Events tables (Table 4, Table 5, Table 6, and Table 8).

**NOTE:** Since subjects in Cohort 3 receive 2 separate infusions, a 24-hour post-infusion follow-up visit will be scheduled after each infusion.

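### Table 8 schedules only an abbreviated physical exam at the second Cohort 3 infusion and 24 hours later, where Sections 8.2.2 and 8.3.1 require a complete one

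*Protocol*

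**What the plan says.** Section 8.2.2 governs both Cohort 3 infusion visits, on Study Days 1 and 15. Its opening rule is "At the time of each scheduled Infusion Visit, the prior activities and procedures must be completed for each subject before infusion may begin". One of the listed procedures is: "Conduct a complete physical examination that includes measurement of weight, and vital signs". The same item adds a heart-and-lung evaluation, a basic neurological evaluation, and a check for DVT, cardiac ischemia or PE.

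Section 8.3.1 covers the 24-hour visit for all three cohorts and lists: "Conduct a complete physical examination that includes measurement of, body weight, and vital signs", with the same further elements. Its note on Cohort 3 says that "a 24-hour post-infusion follow-up visit will be scheduled after each infusion".

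Table 8 in Section 6.5 marks the complete exam at Visits 1, 3 and 4 only. The row "Abbreviated Physical Exam" is marked at the collection visits and at Visits 5, 6, 7, 8 and 9. Visit 6 is the second infusion and Visit 7 is the 24-hour visit after it. Footnote D defines the lesser exam: "Abbreviated physical exam to include vital signs" plus a general health assessment. Footnote C defines the complete exam as adding weight "and a targeted assessment of health as described in section 7.2 and section 8.2".

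**The concern.** Two current parts of the protocol give the site different instructions for the same two visits. Staff working from the schedule would omit, before the second 3-unit infusion and again a day later, an examination that the text makes a condition of infusing.

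Cohort 3 receives the highest dose in a study the protocol describes as first-in-human. In Arm 6 the second infusion is the subject's only exposure to FDP. Section 5.6.1.4 names circulatory overload, fluid in the lungs and swollen extremities among the possible risks of plasma or excess fluid. Weight and a heart-and-lung examination bear directly on these, and Table 8 drops both as named elements. Section 8.2.2 also lets the investigator withhold an infusion on clinical grounds; at infusion 2 that decision would rest on the lesser exam.

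A secondary point concerns the crossover. Under Table 8 the 24-hour examination is less thorough in period 2 (Visit 7) than in period 1 (Visit 4), so the depth of examination is tied to period.

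**Working it through.** The plan gives no figure to reproduce. The check sets text against schedule and then counts.

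**Text against schedule, Cohort 3**

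| Visit | Study Day | Text | Table 8 |
|---|---|---|---|
| 3, infusion 1 | 1 | complete (8.2.2) | complete |
| 4, 24 hours | 2 | complete (8.3.1) | complete |
| 6, infusion 2 | 15 | complete (8.2.2) | abbreviated |
| 7, 24 hours | 16 | complete (8.3.1) | abbreviated |

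This is not a fault of text extraction. Both exam rows line up with the table's column headings, and at Visits 6 and 7 the abbreviated row is positively marked while the complete row is blank.

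**Which source governs exam type?** Sections 8.2.2 and 8.3.1 defer to the schedule tables for urine and blood samples, not for the examination. Footnote C of Table 8 refers back to Section 8.2 for what the complete exam contains. Tables 4, 5 and 6 mark a complete exam at infusion and at 24 hours for Cohorts 1 and 2, and Table 8 does so for infusion 1. Only the second Cohort 3 infusion departs, and no reason is given.

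**Exams affected.** Inputs: 8 Cohort 3 subjects (Table 3); 4 visits each from the table above.
- Required by the text: 8 × 4 = 32.
- Marked in Table 8: 8 × 2 = 16.
- Unscheduled: 32 − 16 = 16, of which 8 fall before infusion 2 and 8 fall 24 hours after it.

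**Infusions affected.** Planned infusions: 8 (Cohort 1) + 8 (Cohort 2) + 8 × 2 (Cohort 3) = 32. Second Cohort 3 infusions: 8, and 8/32 = 25%. By product these are 4 FFP (Arm 5) and 4 FDP (Arm 6). The 4 FDP infusions are half of the 8 planned at 3 units.

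**Age of the last complete exam at infusion 2.** Under Table 8 this is the Visit 4 exam on Day 2. The two-week minimum between infusions (Synopsis; SAP Section 2.2.3) makes Day 15 the earliest date, and the 3-day window makes Day 18 the latest. The gap is therefore 15 − 2 = 13 days to 18 − 2 = 16 days. An abbreviated exam on Day 8 falls within it.

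**What remains at Visits 6 and 7.** Table 8 still schedules vital signs, D-dimer and the Wells scale; footnote H reads "Subjects assessed for DVT, PE, and cardiac ischemia using the Wells Scale prior to infusion, at 30 minutes, 4 hours, and 24 hours". Section 8.2.2 still requires a focused physical evaluation before release. The elements without a scheduled place are weight and the targeted heart-and-lung and neurological examination before infusion and at 24 hours, including the physical-exam part of the DVT check.

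**The case against.** The strongest reply is that the table may be right and the text wrong. Table 8 does not merely omit a mark; it places one in the abbreviated row at both visits, which could be a deliberate lighter exam for a subject examined two weeks earlier. Tables 4 to 6 cannot settle this, since Cohorts 1 and 2 have only one infusion. Nor is Section 8.2.2 flawless. It repeats much of 8.2.1, asks for history since the collection visits (which suits infusion 1 better than infusion 2), and lists the DAT at 30 minutes and 4 hours, where Tables 9, 11 and 15 do not. For Visit 7 the text is also less explicit: the note in 8.3.3 says that its procedures apply to the second visit, and the note in 8.3.1 does not.

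Second, the safety loss is limited. Beyond the checks already listed, Section 10.5.1 has a physician assess side effects through a focused review and physical exam, and Table 8 marks AE assessment at both visits. A site following the text would do the full exam anyway, and the Manual of Procedures, which is not available here, may clarify. Dose is fixed, so weight does not alter it. Physical-exam findings are not a listed endpoint.

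The limits on harm stand and keep this from being more serious. The argument about direction shows that a deliberate lighter exam is conceivable, but nothing in the protocol says so, while the text says the opposite in mandatory terms for every infusion visit. The 8.3.1 note is less explicit, but the section covers all cohorts and provides one procedure list for the 24-hour visit, so requiring the complete exam at Visit 7 is the natural reading.

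**Conclusion.** The concern holds. Table 8 contradicts Sections 8.2.2 and 8.3.1 at Visits 6 and 7, leaving 16 of 32 required complete exams unscheduled around 8 of 32 planned infusions. The counts assume 8 Cohort 3 subjects completing both infusions and a site that follows the table; if staff follow the text, no exam is lost. Because both sequences share the pattern, neither FDP nor FFP gains a net advantage, and the scheduled vital-sign and laboratory endpoints are unaffected. This should be corrected because it concerns a mandatory safety check at the highest dose; it does not threaten the planned analyses.

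**What to change.** In Table 8, mark Visits 6 and 7 in the complete-exam row and clear them from the abbreviated row. Correct the table rather than the text: this restores the stated precondition for infusing and has both infusions examined alike. If the sponsor did intend a lighter exam at infusion 2, Sections 8.2.2 and 8.3.1 would have to say so and give the reason.

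The cost is two columns in two rows of one table. In practice 8 subjects × 2 visits = 16 abbreviated exams become complete ones, at visits already planned, with no new visit or sample.

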### 8.3. Follow-Up Visits

#### 8.3.1. 24-Hour Follow-Up Visit

Subjects in all 3 cohorts should be scheduled for an on-site follow-up visit 24 hours ( $\pm$  3 hours) after the completion of the plasma infusion. During this visit, the following procedures will be performed:

- Review of medical history, concomitant medications, and AEs since the infusion visit;
- Conduct a complete physical examination that includes measurement of, body weight, and vital signs (blood pressure, heart rate, respiration rate, and temperature), and evaluation of cardiopulmonary systems, basic neurological function, and presence of DVT, cardiac ischemia, or PE. DVT will be assessed in conjunction with a subjects' D-Dimer test results and Wells scale score; and
- Collect urine and blood samples as noted for all tests listed in the Schedule of Events tables (Table 4, Table 5, Table 6, and Table 8).

**NOTE:** Since subjects in Cohort 3 receive 2 separate infusions, a 24-hour post-infusion follow-up visit will be scheduled after each infusion.

## 8.3.2. Telephone Follow-Up

In addition to scheduled on-site follow-up visits, subjects in all 3 cohorts will be contacted by phone at 48 hours ( $\pm$  2 hours), 72 hours ( $\pm$  2 hours), and 14 days ( $\pm$  2 hours) (ie, Study Days 3, 4, and 15) after the completion of the plasma infusion. During the calls, subjects will be asked specific questions (Appendix H) regarding possible signs and symptoms of any AEs they may have experienced and any concomitant medications taken since the infusion visit. The date and time of the call, as well as the subject's responses will be recorded in the source documents and the eCRF.

Cohort 3 subjects' will have no 14- day follow-up phone call after the first infusion since it would occur on the same day as the second infusion (Study Day 15). The 14-day follow-up phone call subsequent to the second infusion visit will occur on Study Day 29.

# 8.3.3. 7-Day Follow-Up Visit

A post-infusion follow-up visit will be scheduled 7 days ( $\pm$  1 day) post-infusion for subjects in all 3 cohorts. The following procedures will be performed at these visits:

- Review of medical history, concomitant medications, and AEs since the last telephone follow-up contact;
- Abbreviated physical exam which includes vital signs (blood pressure, heart rate, respiration rate, and temperature) and a general assessment of health; and
- Collect blood samples as noted for all tests listed in the Schedule of Events tables (Table 4, Table 5, Table 6, and Table 8).

**NOTE:** Since subjects in Cohort 3 receive 2 separate infusions, a 7-day post-infusion follow-up visit should also be scheduled after the second infusion. The second 7-day post-infusion follow-up visit will also follow the procedures described in this section.

### 8.3.4. 28-Day Follow-Up Visit

A post-infusion follow-up visit will be scheduled 28 days ( $\pm$  1 day) post-infusion for subjects enrolled in Cohorts 1 and 2. For subjects enrolled in Cohort 3, a 28-day post-infusion follow-up visit will take place after the second plasma infusion, only, approximately 42 days after the first infusion visit. The following procedures will be performed at these follow-up visits:

- Review of medical history, concomitant medications, and AEs since the 14-day telephone follow-up contact;
- Abbreviated physical exam which includes vital signs (blood pressure, heart rate, respiration rate, and temperature) and a general assessment of health;
- Collect blood samples as noted for all tests listed in the Schedule of Events tables (Table 4, Table 5, Table 6, and Table 8); and
- Exit interview concluding the subject's study participation.

#### 8.3.5. Biological Samples

Samples collected under this protocol will be used to conduct protocol-related safety and efficacy evaluations as noted in Table 4, Table 5, Table 6, and Table 8. No genetic testing will be performed on these samples. Total volumes, by visit, for laboratory tests performed during the course of the study are listed in Table 7 and Table 9.

Samples will be stored in a quality-controlled environment. Transport and storage of these biological samples will be handled according to the clinical site's SOP. Any study for the future use of these biological samples will have IRB approval. In addition, a subject may decide at any point to withdraw consent for the future use of his or her samples. Should a subject withdraw consent for the use of his or her samples will be destroyed according to the clinical site's SOP.

## 8.4. Early Withdrawal Procedures

Subjects who withdraw from the study at any time before the Infusion Visit who have not experienced an AE will have the Exit Interview administered by telephone. Subjects who withdraw from the study any time after the infusion and before the 7-Day Post-Infusion Follow-Up Visit will be asked to complete all Early Discontinuation Visit procedures to ensure safety and to collect as much data as possible:

- Review of medical history, concomitant medications, and AEs since the telephone follow-up contact;
- Abbreviated physical exam which includes vital signs (blood pressure, heart rate, respiration rate, and temperature) and a general assessment of health; and
- Laboratory tests including:
  - Urinalysis;
  - Urine pregnancy test (females only);
  - CBC (Hematocrit, Hemoglobin, Platelet Count, RBC Count, WBC Count);
  - Chemistry panel (ALP, ALT, AST, Calcium, Chloride, Potassium, Sodium, Lactate, Bicarbonate, Glucose, Total Bilirubin, Total Protein, BUN, and Creatinine);
  - PT/INR and aPTT;
  - DAT;
  - D-dimer; and
  - COHORT 3 ONLY Coagulation factor tests (Factors I, II, V, VII, VIII, IX, X, XI, von Willebrand factor, Protein C activity, and Protein S activity), PF 1+2, TAT, AT-III, alpha-2 antiplasmin, and C3a des Arg. PF 1+2, TAT, AT-III, alpha-2 antiplasmin, and C3a des Arg are for research purposes only and will not be used to assess subject safety.

